2.5 Device Classification and Rationale

The Jabra Enhance Plus device is expected to be classified as a Class II medical device. The results of this pivotal study are intended to support a Traditional 510(k) Premarket Notification for submission to the FDA.

2.6 Device Insurance and Replacement

All investigational devices will be issued to the investigational sites by GN Hearing A/S. Any special procedures, such as calibration and maintenance of the devices, will be conducted per the device labeling provided to study subjects. If a device breaks, malfunctions, or is lost,

replacement devices will be issued to the site by GN Hearing A/S for the patient to continue participation in the study.

2.7 Disposition of the Device

Subjects will be required to utilize their Jabra Enhance Plus device to access the Jabra Enhance app. To access the Jabra Enhance Plus device, enrolled subjects will receive a link from the Sponsor prompting them to download the Jabra Enhance Application (app). Once downloaded, the enrolled subjects will be prompted to create their own secure login credentials to utilize during the study. When subject involvement in the investigational study is completed, the Jabra Enhance Plus app will automatically log the subject out, and their account will no longer be usable. The data for the subject's account will be saved.

3.0 OBJECTIVES OF RESEARCH STUDY

3.1 Hypotheses

3.1.1 In-lab validation component-Primary

- Null hypothesis: Mean $|REAG_{PRO-FIT} - REAG_{SELF-FIT}| \geq 2.5$ dB
- Alternative hypothesis: Mean $|REAG_{PRO-FIT} - REAG_{SELF-FIT}| < 2.5$ dB

3.1.2 In-lab validation component-Secondary

- Null hypothesis: Mean $|QuickSIN_{PRO-FIT} - QuickSIN_{SELF-FIT}| \geq 1.5$ dB
- Alternative hypothesis: Mean $|QuickSIN_{PRO-FIT} - QuickSIN_{SELF-FIT}| < 1.5$ dB

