3.1.4 Wear-Time Field Trial-Secondary

- Null hypothesis: Mean difference $(QuickSIN_{PRO-FIT} - QuickSIN_{SELF-FIT}) \geq 1.5$ dB
- Alternative hypothesis: Mean difference $(QuickSIN_{PRO-FIT} - QuickSIN_{SELF-FIT}) < 1.5$ dB

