3.1.6 In-Lab Session-Reliability Component-Secondary

- Null hypothesis: Mean difference $|QuickSIN_{SELF-FIT A} - QuickSIN_{SELF-FIT B}| \geq 1.5$ dB
- Alternative hypothesis: Mean difference $|QuickSIN_{SELF-FIT A} - QuickSIN_{SELF-FIT B}| < 1.5$ dB

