5.0 STUDY SUBJECTS

5.1 Sample Size Determination

The sample size was powered by the primary outcome measure of the wear-time field trial, the APHAB, as it is the most variable of the outcome measures across all components of this study. When the sample size in each sequence group in the crossover trial is 16 (giving a total sample size of 32), a crossover design will have 80% power to reject the null hypothesis that the SELF-FIT APHAB mean is inferior to the PRO-FIT APHAB mean based on the mean difference, in favor of the alternative hypothesis that the SELF-FIT mean is non-inferior to the PRO-FIT mean, assuming that the expected difference in means is 0, the non-inferiority difference margin is .084 (or 8.4%), the Crossover ANOVA \sqrt{MSE} is 0.115 (or 11.5%) (giving a standard deviation of differences, σ , of 0.163 or 16.3%) and that the test is made at the 2.5% significance level.

The overall design for the in-lab session is a repeated-measures design comparing outcomes for three procedures: SELF-FIT A, SELF-FIT B, PRO-FIT. Given that SELF-FIT A and B are the same procedure repeated two times, this results in three possible procedure sequences: (1) SELF-FIT A, SELF-FIT B, PRO-FIT; (2) SELF-FIT A, PRO-FIT, SELF-FIT B; and (3) PRO-FIT, SELF-FIT A, SELF-FIT B. An equal number of subjects will receive each sequence at each site to ensure full counterbalancing of order. A total of 36 subjects, 18 per site, will be included which meets the minimum of 32 required for sufficient statistical power, achieves the desired counterbalancing, and allows for some subject attrition or missing data.

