6.2.7 QuickSIN

The subject will be seated in a sound-attenuated booth facing a single loudspeaker. All QuickSIN measures, unaided and aided, will be binaural. The QuickSIN test consists of lists of six sentences that will be played from that loudspeaker at a constant level of 65 dB SPL (at location of subject's head using the method of substitution). This speech level was chosen as one approximating a typical conversational level (60-65 dB SPL) and matching the speech input level used for the REAR measures (65 dB SPL). The level of the co-located background four-talker babble increases across the six sentences for signal-to-noise ratios (SNRs) ranging from +25 to 0 dB SNR (in steps of 5 dB). The subject is asked to repeat each sentence. The audiologist scores whether the subject correctly repeated the predetermined key words in each sentence. The resulting score is interpreted as an SNR loss where a value near 0 indicates better hearing and larger values indicate more difficulty listening in noise.

There are 18 lists of the QuickSIN, but McArdle and Wilson (2006) found four of these to be non-equivalent to the others. The remaining 14 lists will be used as follows. Before the first QuickSIN measure at the end of the initial screening (Visit 1), two lists will be presented as practice lists (Lists 4 and 5). For the remaining 12 lists (Lists 1-3, 6, 8-12, 15, 17, 18), two will be assigned to each of the following conditions: unaided (during initial screen; to permit measures of relative benefit), in-lab initial SELF-FIT A, in-lab initial SELF-FIT B, in-lab initial PRO-FIT (the condition order and list pair assigned for each condition will be randomized for each participant), at end of first 10-to-14-day wear period (Visit 2; either final SELF-FIT A or final PRO-FIT), and at end of

final 10-to-14-day wear period (Visit 3; either final PRO-FIT or final SELF-FIT A). Each QuickSIN score will be based on two lists, 60 keywords, and no lists will be repeated for a given subject.

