6.2.7.1 QuickSIN Test Procedure

Four conditions: **Unaided, Self-Fit A, Self-Fit B, Pro-Fit**

- i. Listener will sit in a chair in the center of a sound-treated booth facing the speaker from which the test materials will be elicited (0 degrees azimuth, 1 meter distance).
- ii. Training: To familiarize subjects with the speech task, listeners will be presented with two practice lists (Lists 4 and 5) before commencing with the experimental protocol (Visit 1, Unaided only).
- iii. The test will be presented in a sound field at 65 dB SPL.
- iv. There are six sentences in each list of the QuickSIN and 5 keywords that are scored per sentence, resulting in a total of 30 keywords scored per list. Speech levels are automatically presented at SNRs of +25, +20, +15, +10, +5 and 0 dB, one SNR per sentence. The signal-to-noise ratio (SNR) for which 50% of the presented words are intelligible is calculated by subtracting the number of words correct (out of 30) for a given list from 25.5 (Killion *et al.*, 2004).
- v. The microphone setting will be set to "Wide" (omni-directional) during these measurements.

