8.1.3 In-Lab *QuickSIN Test - Validity* (initial Pro-Fit vs. initial Self-Fit A)

- i. Paired-sample t-test for equivalence of the means of the initial-fit settings of the SELF-FIT A procedure to initial-fit settings of the PRO-FIT procedure
- ii. Supplementary analyses will include examination of the distribution of differences in dB between the QuickSIN threshold SNRs for initial-fit settings of the SELF-FIT A procedure and the initial-fit settings of the PRO-FIT procedure, as well as computation of correlation coefficients between the threshold SNRs for each method.

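### The in-lab QuickSIN hypotheses limit a mean absolute difference, while the planned tests address equivalence of means; with identical fits the two can give opposite answers

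*Combined protocol and SAP*

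**What the plan says.** Two in-lab secondary hypotheses put absolute-value bars inside the mean. For validity, section 3.1.2 has the alternative "Mean $|QuickSIN_{PRO-FIT} - QuickSIN_{SELF-FIT}| < 1.5$ dB". For reliability, section 3.1.6 has "Mean difference $|QuickSIN_{SELF-FIT A} - QuickSIN_{SELF-FIT B}| < 1.5$ dB". The wear-time hypothesis in 3.1.4 uses the same number without bars: "Mean difference $(QuickSIN_{PRO-FIT} - QuickSIN_{SELF-FIT}) < 1.5$ dB".

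The analysis section reads differently. Section 8.1.3 plans a "Paired-sample t-test for equivalence of the means of the initial-fit settings of the SELF-FIT A procedure" against PRO-FIT, and 8.1.1 plans a paired equivalence t-test for QuickSIN between SELF-FIT A and B. The synopsis says that mean absolute differences will be reported.

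On scoring, section 6.2.7.1 presents sentences at "SNRs of +25, +20, +15, +10, +5 and 0 dB, one SNR per sentence", with five keywords each, and obtains the list score by "subtracting the number of words correct (out of 30) for a given list from 25.5". Section 6.2.7 adds: "Each QuickSIN score will be based on two lists, 60 keywords, and no lists will be repeated for a given subject".

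On sample size, section 5.1 powers the trial on APHAB "as it is the most variable of the outcome measures across all components of this study". The synopsis states that 36 subjects give about 80% power at the 0.05 level to rule out non-equivalence of SELF-FIT A and B, or of SELF-FIT A and PRO-FIT. No section gives a QuickSIN SD, a retest error, a QuickSIN power calculation or a basis for 1.5 dB.

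**The concern.** A signed mean difference is centred on zero when two fits are the same. A mean absolute difference is not, because it accumulates the measurement noise of both scores. So 1.5 dB on the signed mean and 1.5 dB on the mean absolute difference are requirements of very different stringency, although the plan uses the figure for both.

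If the literal hypotheses govern, the two in-lab criteria judge the retest noise of QuickSIN as well as the fit. A self-fit identical to the professional fit could then be reported as not equivalent, and a repeatable self-fit as not reliable, in a study meant to support a 510(k) submission (section 2.5). If section 8.1 governs, this does not arise. The plan does not say which governs.

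**Working it through.** **The plan's own calculation.** Section 5.1 uses a 2x2 crossover non-inferiority t-test with root MSE 0.115, margin 0.084, true difference 0 and a 2.5% level. The SD of differences is 0.115 × √2 = 0.163. With N = 32, the noncentral t with 30 df gives power 0.807, and 32 is the smallest even N that reaches 80%. The APHAB figure is reproduced. It concerns a signed mean.

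**The floor of the absolute criterion.** Let D be the within-subject difference of two QuickSIN scores under identical fits, roughly normal with mean 0 and standard deviation SD. Then:
- mean |D| = √(2/π) × SD = 0.798 × SD
- SD of |D| = √(1 − 2/π) × SD = 0.603 × SD

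Mean |D| equals 1.5 dB when SD = 1.5 / 0.798 = 1.88 dB.

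**Testing the literal hypothesis.** Rejecting the null at one-sided 5% with n = 36 needs mean |D| + t(0.95, 35) × SD of |D| / 6 below 1.5. At its expected value the left side is 0.798 SD + 1.690 × 0.603 SD / 6 = 0.968 SD. The chance of passing is therefore about one half at SD = 1.5 / 0.968 = 1.55 dB. At one-sided 2.5% the same step gives 1.50 dB. The documents do not state the sidedness of the 0.05 level.

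Simulated pass probabilities for one criterion (normal D, n = 36, one-sided 5%):

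| SD of D (dB) | Mean abs. D (dB) | Literal criterion | Signed ±1.5 dB |
|---|---|---|---|
| 1.2 | 0.96 | 0.99 | 1.00 |
| 1.4 | 1.12 | 0.82 | 1.00 |
| 1.6 | 1.28 | 0.41 | 1.00 |
| 1.8 | 1.44 | 0.13 | 0.999 |
| 2.0 | 1.60 | 0.03 | 0.994 |

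**What SD the documented scoring implies.** One list has variance Σ 5p(1 − p) over the six SNRs. Averaging two lists halves this, and differencing two such scores doubles it, so the variance of D equals that single-list sum. For a logistic curve with slope s at 50%, the sum at 5 dB spacing is about 1/(4s). At s = 0.10 per dB this gives SD = √2.5 = 1.58 dB. Simulation over the actual SNRs gives 1.56 dB.

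The slope, the within-sentence word correlation and the 50% points (spread over 2-12 dB) are assumptions, because the plan gives none of them. Results for identical fits, n = 36, one-sided 5%:

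| Slope per dB | Correlation | SD of D | Mean abs. D | One passes | Both fail | Signed ±1.5 |
|---|---|---|---|---|---|---|
| 6% | 0 | 1.92 | 1.52 | 0.05 | 0.90 | 0.996 |
| 8% | 0 | 1.72 | 1.36 | 0.23 | 0.61 | 1.00 |
| 10% | 0 | 1.56 | 1.23 | 0.52 | 0.28 | 1.00 |
| 12% | 0 | 1.43 | 1.13 | 0.77 | 0.08 | 1.00 |
| 15% | 0 | 1.29 | 1.01 | 0.96 | 0.004 | 1.00 |
| 6% | 0.1 | 2.27 | 1.81 | 0.002 | 0.996 | 0.974 |
| 8% | 0.1 | 2.02 | 1.60 | 0.02 | 0.95 | 0.991 |
| 10% | 0.1 | 1.83 | 1.45 | 0.10 | 0.81 | 0.998 |
| 12% | 0.1 | 1.69 | 1.34 | 0.27 | 0.56 | 1.00 |
| 15% | 0.1 | 1.52 | 1.20 | 0.58 | 0.21 | 1.00 |

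These figures contain word-scoring chance only. Differences between lists, or in attention, would add to the SD.

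**Does the remark that APHAB is most variable cover QuickSIN?** On the signed scale, SD over margin is 0.163 / 0.084 = 1.94 for APHAB. For QuickSIN it is 1.29 / 1.5 = 0.86 to 2.27 / 1.5 = 1.51. The remark holds there under these assumptions. It does not carry over to the absolute criterion, where noise raises the tested quantity itself.

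**The case against.** The strongest reply is that section 8.1 is the analysis plan. Section 8.1.3 names equivalence of means, so the bars in 3.1.2 and 3.1.6 may be loose notation for a two-sided equivalence hypothesis. On that reading identical fits pass nearly always, n = 36 is ample for QuickSIN, and much of the remedy is already planned. This is a fair reading, and it limits the point to a mismatch between hypotheses and analysis. It does not remove the mismatch: the bars stand inside the mean in the formal hypotheses, 3.1.4 omits them, the synopsis speaks of mean absolute differences, and nothing gives section 8.1 precedence. Sections 1.5.3.1 and 8.4 also use mean absolute differences, but for REAG.

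A second reply is that the plan states no confidence-bound rule for the absolute criterion. That stands. If only the observed mean had to fall below 1.5 dB, identical fits would pass about 99% of the time at an SD of 1.4 dB, 80% at 1.7 dB and about half at 1.88 dB.

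A reader might go further and infer that 1.5 dB lies at the noise floor, so that identical fits would usually fail both criteria. The documents do not support that, because the answer turns on an SD they do not give. Both criteria fail more often than not only from an SD of roughly 1.65-1.7 dB, and at 1.4 dB or below identical fits usually pass.

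**Conclusion.** The point holds as an inconsistency. The hypotheses in 3.1.2 and 3.1.6 and the tests in 8.1.1 and 8.1.3 are different criteria that can reach opposite conclusions on the same data. Taken literally and tested at one-sided 5% with n = 36, the hypotheses give identical fits a chance of passing one criterion between under 1% and about 96%, and below 50% once the SD of the difference exceeds about 1.55 dB. The signed test gives 97-100%. The range rests on assumed slopes of 6-15% per dB and word correlation of 0-0.1. The existence of a floor does not depend on those assumptions.

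The synopsis's power of about 80% cannot be taken to cover the literal QuickSIN criteria. This is no error in the APHAB calculation, which reproduces.

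A reader might also infer that a QuickSIN failure would sink the study. It would not: section 8.4 defines overall success by the primary endpoints, and both criteria here are secondary. The consequence is limited to how those results are reported and read.

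**What to change.** Restate 3.1.2 and 3.1.6 as two-sided equivalence of the signed mean QuickSIN difference within ±1.5 dB, matching 8.1.1 and 8.1.3. State the significance level with its sidedness, the assumed SD of the difference and the basis for 1.5 dB on that scale.

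Report the mean absolute SELF-FIT A versus PRO-FIT difference descriptively beside the mean absolute A versus B difference. The second shows how much absolute difference arises when the same procedure is repeated.

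The cost is wording in two hypotheses, with no new data or visits. The downside is that a signed mean alone says nothing about agreement within individuals. The distributions of differences and the correlations already planned in 8.1.1 and 8.1.3 should therefore stay.

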3.1.3 Wear-Time Field Trial-Primary

- Null hypothesis: Mean difference $(APHAB_{PRO-FIT} - APHAB_{SELF-FIT}) \geq .084$
- Alternative hypothesis: Mean difference $(APHAB_{PRO-FIT} - APHAB_{SELF-FIT}) < .084$

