3.2 Study Endpoints

3.2.1 Primary Effectiveness Endpoint(s)

For the validation component of the immediate in-lab session comparisons, Real-Ear Aided Gain (REAG) will be measured using both an audiology-best-practices (professional) hearing aid fitting (PRO-FIT) and a self-fitting method (SELF-FIT).

- Success criterion is defined as SELF-FIT REAG is equivalent to PRO-FIT NAL-NL2 prescription REAG targets based on the average real-ear aided gain at 500, 1000, 2000 and 4000 Hz.

For the reliability component of the immediate in-lab session comparisons, Real-Ear Aided Gain (REAG) will be measured twice (A, B) using the SELF-FIT method.

- Success criterion is four-frequency average REAG for SELF-FIT B is equivalent to the REAG for SELF-FIT A based on the average real-ear aided gain at 500, 1000, 2000 and 4000 Hz.

For the wear-time crossover field trial, the APHAB will be measured following both an audiology best-practices hearing aid fitting (PRO-FIT) and a self-fitting method (SELF-FIT).

- Success criterion is defined as SELF-FIT APHAB global score is non-inferior to PRO-FIT APHAB global scores following completion of the wear-time field trial.

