3.2.3 Secondary Effectiveness Endpoints

For the validation component of the immediate in-lab session comparison, aided QuickSIN performance will be compared between SELF-FIT and PRO-FIT.

- Success criterion is the SELF-FIT QuickSIN speech-recognition threshold in noise (signal-to-noise ratio, SNR) is equivalent to that of PRO-FIT.

For the reliability component of the immediate in-lab session comparison, QuickSIN performance will be measured twice (A, B) using the SELF-FIT method to assess test-retest reliability.

- Success criterion is QuickSIN thresholds are equivalent for SELF-FIT A and B.

For the wear-time crossover field trial, QuickSIN performance will be compared between SELF-FIT and PRO-FIT.

- Success criterion is defined as SELF-FIT QuickSIN SNR is equivalent to PRO-FIT QuickSIN SNR following completion of the wear-time field trial.

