6.2.8 APHAB

The APHAB is a 24-item self-assessment inventory in which the subject reports the amount of trouble they are having with communication or noises in various everyday situations. Benefit from a hearing aid is calculated by comparing the subject's unaided score to their aided score. Although it is possible to collect unaided and aided scores at the same time by asking the subject to reflect back on unaided listening, we will obtain unaided APHAB scores during Visit 1 prior to initiation of the cross-over wear-time trial.

A sample question is as follows: "When I'm at the dinner table with several people, and I am trying to have a conversation with one person, understanding speech is difficult." For each of the 24 items the subject is asked to select one of the following percentages to indicate how frequently this occurs: Always (99%); Almost Always (87%); Generally (75%); Half-the-time (50%); Occasionally (25%); Seldom (12%); or Never (1%). The APHAB will be administered and scored via a tablet PC or iPad.

The APHAB produces scores for 4 subscales: Ease of Communication (EC), Reverberation (RV), Background Noise (BN), and Aversiveness (AV). To increase reliability, only an APHAB-global score based on all 24 items will be used here.

Three conditions: Unaided (Visit 1), Aided (Visit 2), Aided (Visit 3). These three conditions are: 1) prior to the onset of the wear-time field trial, 2) after the first 10-14-day wear period with the first fitting settings (final-fit SELF-FIT A or final-fit PRO-FIT), and 3) after the second 10-14-day wear period with the other fitting settings (final-fit PRO-FIT or final-fit SELF-FIT A).

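### The wear-time non-inferiority hypotheses for APHAB and QuickSIN point the wrong way for scores on which higher is worse

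*Combined protocol and SAP*

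**What the plan says.** Section 3.1.3 gives the wear-time primary hypothesis on APHAB as "Alternative hypothesis: Mean difference $(APHAB_{PRO-FIT} - APHAB_{SELF-FIT}) < .084". Section 3.1.4 gives the secondary one as "Alternative hypothesis: Mean difference $(QuickSIN_{PRO-FIT} - QuickSIN_{SELF-FIT}) < 1.5$ dB". Both are one-sided, with no lower bound and no absolute value.

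The direction of the scores is set out in section 6.2:

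- **APHAB (6.2.8):** "the subject reports the amount of trouble they are having with communication or noises in various everyday situations". Answers run from Always (99%) to Never (1%), and the sample item is a statement of difficulty. The section adds that "only an APHAB-global score based on all 24 items will be used here".
- **QuickSIN (6.2.7):** "a value near 0 indicates better hearing and larger values indicate more difficulty listening in noise".

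Section 3.2.1 states the intent in words: "SELF-FIT APHAB global score is non-inferior to PRO-FIT APHAB global scores". Section 5.1 agrees, since its null is that the SELF-FIT APHAB mean is inferior. Sections 8.1.4 and 8.1.5 name a non-inferiority t-test for the 2 x 2 crossover, without giving the direction of subtraction or the bound to be compared with the margin.

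For wear-time QuickSIN, section 3.2.3 says "Success criterion is defined as SELF-FIT QuickSIN SNR is equivalent to PRO-FIT QuickSIN SNR following completion of the wear-time field trial", and the synopsis agrees. Sections 3.1.4 and 8.1.5 give a one-sided non-inferiority test.

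**The concern.** When higher is worse, SELF-FIT is non-inferior if SELF-FIT minus PRO-FIT is below the margin. Sections 3.1.3 and 3.1.4 subtract the other way. The worse SELF-FIT is, the more negative PRO-FIT minus SELF-FIT becomes, and the more easily the alternative is accepted. What the test guards against is a SELF-FIT that is better by the margin.

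APHAB is the primary field-trial endpoint and the one the study is powered on. Section 8.4 makes overall success depend on meeting all primary endpoints. A test run as section 3.1.3 is written gives no protection against an inferior SELF-FIT and would penalise a superior one. The results are meant to support a 510(k) submission (section 2.5), and correcting the sign after the data are seen would be a post-hoc change to a primary hypothesis.

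**Working it through.** **Inputs (section 5.1).** Margin 0.084; crossover root MSE 0.115; expected difference 0; significance level 2.5%, taken as one-sided; 16 per sequence (32 in total) for power; 36 planned.

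**Method.** For a 2 x 2 crossover with N subjects, SE = 0.115 × √(2/N) and df = N − 2. Let d be the true PRO-FIT minus SELF-FIT. The rule as written passes when (observed difference − 0.084)/SE falls below −t(0.975, df). Its probability comes from the non-central t distribution with non-centrality (d − 0.084)/SE. The corrected rule uses SELF-FIT minus PRO-FIT, which replaces d by −d.

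**Step 1: reproduce the plan's figure.**

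- SD of differences = 0.115 × √2 = 0.163, as stated.
- At N = 32, SE = 0.115 × √(2/32) = 0.02875, df = 30, and the non-centrality at d = 0 is −0.084/0.02875 = −2.92. Power is 80.7%, which matches the stated 80%.
- A one-sided 5% level would give 88.7%, so one-sided 2.5% is the basis used.

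**Step 2: pass probability at N = 36** (SE = 0.115 × √(2/36) = 0.0271, df = 34), on the raw aided APHAB score.

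| True state of SELF-FIT | d = PRO − SELF | As written | Correct direction |
|---|---|---|---|
| 20 points worse | −0.20 | about 100% | about 0% |
| 12 points worse | −0.12 | about 100% | 0.06% |
| 8.4 points worse (the margin) | −0.084 | 99.998% | 2.5% |
| Equal | 0 | 85.3% | 85.3% |
| 5 points better | +0.05 | 22.9% | 99.8% |
| 8.4 points better | +0.084 | 2.5% | 99.998% |

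At N = 32 the pattern is the same: 8.4 points worse passes 99.99% as written, equal passes 80.7%, and 5 points better passes 20.8%.

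**Step 3: cut-off on the observed difference.** At the planned variability, the rule as written passes when observed PRO-FIT minus SELF-FIT is below 0.084 − t × SE:

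- N = 36: 0.084 − 2.032 × 0.0271 = 0.029
- N = 32: 0.084 − 2.042 × 0.02875 = 0.025

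With 36 subjects, an observed SELF-FIT advantage above about 2.9 points fails, while any observed disadvantage passes.

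**Step 4: QuickSIN.** The documents give neither an SD nor a significance level for this comparison. I assume an SD of differences of 1.5 to 3 dB, N = 36 and one-sided 2.5%. For a SELF-FIT truly 3 dB worse, d − margin = −3 − 1.5 = −4.5 dB. SE runs from 1.5/√36 = 0.25 to 3/√36 = 0.5 dB, so the non-centrality runs from −18 to −9. The rule as written passes with probability about 1.00 throughout. The reversal itself does not depend on these assumptions.

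**The case against.** The strongest objection is that APHAB may have been meant as a benefit score. Sections 1.5.3.1 and 8.4 call it a self-report measure of benefit, and section 6.2.8 explains that benefit compares unaided with aided scores and schedules an unaided APHAB at Visit 1. On unaided minus aided, higher is better and section 3.1.3 is correctly signed. This reading is possible but has the weaker support. No hypothesis, endpoint or analysis names benefit as the tested variable. Section 3.2.1 names the global score, section 6.2.5 specifies aided APHAB at Visits 2 and 3, and section 8.1.4 analyses global scores for the final-fit settings. Even if benefit was intended, the primary variable is undefined and the text must change. The reading does not help section 3.1.4, because section 8.1.5 analyses QuickSIN threshold SNRs, whose direction section 6.2.7 states outright.

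A second objection is that the intent is clear in words (sections 3.2.1, 5.1 and 8.4), so an analyst would probably do the right thing. It is fair that the error rates above apply only if the symbols are followed. But the reversed formulas are the only formal statement of the hypotheses, and section 8.1 does not correct them.

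Three smaller points stand. Wear-time QuickSIN is secondary and does not decide overall success. Its significance level is not stated anywhere. The conflict between equivalence and non-inferiority for QuickSIN is a separate defect that happens to need the same edit.

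**Conclusion.** Wrong as written. Read on raw aided scores, sections 3.1.3 and 3.1.4 reverse the non-inferiority test and contradict the plan's own null in section 5.1 and criterion in section 3.2.1. For APHAB, the probability of declaring success when SELF-FIT is inferior by exactly the margin is 99.998% at N = 36, where 2.5% was intended. The size rests on the plan's root MSE, margin and one-sided 2.5% level, and on the tested variable being the aided global score. The QuickSIN reversal is unambiguous; only its illustrative probability uses an assumed SD and significance level. The stated power and sample size are unaffected, because the assumed difference is zero and the calculation is symmetric there. This must be fixed before analysis.

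**What to change.** 1. **Section 3.1.3:** H0: mean (APHAB SELF-FIT − APHAB PRO-FIT) ≥ 0.084; H1: < 0.084. If benefit was intended, keep the present order but define the variable as unaided minus aided APHAB in sections 3.1.3, 3.2.1 and 8.1.4.
2. **Section 3.1.4:** H0: mean (QuickSIN SELF-FIT − QuickSIN PRO-FIT) ≥ 1.5 dB; H1: < 1.5 dB.
3. **Sections 8.1.4 and 8.1.5:** state that higher is worse and that success means the upper one-sided confidence bound for SELF-FIT minus PRO-FIT lies below the margin. For APHAB the bound is 97.5%, matching section 5.1. For QuickSIN the sponsor must state the level; 97.5% would be consistent.
4. **Section 3.2.3 and the synopsis:** change the wear-time QuickSIN criterion to non-inferior, in line with sections 8.1.5 and 8.4. If equivalence is really wanted, sections 3.1.4 and 8.1.5 need a test against both bounds instead.

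The cost is wording in these sections, made as a dated amendment before the wear-time data are analysed. Sample size, data collection and conduct stay as they are: corrected power at zero difference is still 80.7% with 32 subjects and 85.3% with 36. Only a switch of QuickSIN to equivalence would call for a separate look at power.
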